8.3.1.2. Representativeness of doctor and patient samples

The participating doctors will be described. Comparisons will be made between doctors who have participated actively in the study (included at least one patient) and doctors who were not active or who refused to participate. Patients who are lost to follow-up during the study (who leave the study with no information on whether or not treatment was continued or on death) will be compared to the patients who are monitored until the event date (progression, death or end of treatment) or the end date of 2 years.

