9.1.2. Patients lost to follow up during the study

There will be a particular focus on patients who leave the study, or who the investigator does not see again for a visit due to the observational nature of the study (the frequency of visits for patient follow-up can vary from one doctor to another). For patients who are lost to follow-up, a last visit/anticipated end of study questionnaire will be completed by the investigator. The statistical analyses will compare the characteristics of the enrolled patients who participate in the whole duration of the study with the enrolled patients who were later lost to follow-up and/or left the study.

[figure not shown]

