5.4.3. Representativeness of Samples of Doctors and Patients

Comparisons will be made between active doctors who took part in the study (who included at least one patient) and inactive doctors who did not include any patients, by calculating standardised differences.

These standardised differences will be calculated as follows:

Type of variable	Equation			
Qualitative	$d = \frac{P_1 - P_2}{\sqrt{\frac{P_1(1 - P_1) + P_2(1 - P_2)}{2}}}$			
	P ₁ : proportion of individuals with the feature in group 1			
	P ₂ : proportion of individuals with the feature in group 2			
Quantitative	$d = \frac{\text{moy}_1 - \text{moy}_2}{\sqrt{\frac{\text{var}_1 + \text{var}_2}{2}}}$			
	mean ₁ : mean in group 1			
	mean ₂ : mean in group 2			
	var ₁ : variance in group 1			
	var ₂ : variance in group 2			

Similarly, comparisons will be made between included and non-included patients based on information collected in the non-inclusion register (age, sex), The reasons for non-inclusion will be presented. The "others" reasons for non-inclusion will be listed.

In addition, patients who are lost to follow-up and/or dropped out of the study (for a reason other than death) will be compared to patients with complete follow-up (follow-up until progression, death, end of main treatment ongoing at the time of inclusion or 2-year cutoff date) in the reference set.

We will deem the observed difference to be small if the standardised difference is between [0.2 and 0.3], average if between [0.3-0.8] and large if it is over 0.8. A value of 0.2 or less will be considered to represent no difference.

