6.1.2. Patients Lost to Follow-up During the Follow-up Period

Particular attention will be paid to patients who stop the study or whom the investigator does not review in a visit because of the observational nature of the study (visit frequency for patient follow-up may vary depending on the doctor). For patients who are lost to follow up, an early last news/end of study questionnaire will be completed by the investigator. The statistical analyses will compare the characteristics of included patients who participated throughout the duration of the study with those patients who were included but were lost to follow-up and/or stopped the study.

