9.1.4.3. Representativeness of the Samples of Patients and Doctors

Table 14.1.4.3.1: Representativeness of Sample of Doctors

		Active doctors (N=XX)	Inactive doctors (N=XX)	Standardised difference*
Specialty	N	XX	XX	
-p	Missing data	XX	XX	
	Oncology	XX (XX.X%)	XX (XX.X%)	XX.X
	Gastroenterology	XX (XX.X%)	XX (XX.X%)	XX.X
	Endocrinology	XX (XX.X%)	XX (XX.X%)	XX.X
	Other	XX (XX.X%)	XX (XX.X%)	XX.X
Type of practice	N	XX	XX	
31 1	Missing data	XX	XX	
	Public	XX (XX.X%)	XX (XX.X%)	XX.X
	Private	XX (XX.X%)	XX (XX.X%)	XX.X
Type of facility	N	XX	XX	
- 5	Missing data	XX	XX	
	Hospital	XX (XX.X%)	XX (XX.X%)	XX.X
	Primary care/clinic	XX (XX.X%)	XX (XX.X%)	XX.X
	Cancer Centre	XX (XX.X%)	XX (XX.X%)	XX.X

Table 14.1.4.3.1: Representativeness of Sample of Doctors

		Active doctors (N=XX)	Inactive doctors (N=XX)	Standardised difference*
Estimated number of patients suffering from a pancreatic neuroendocrine tumour (treated at the time the participation agreement was completed)	N	XX	XX	
1 /	Missing data Mean (SD) Median [Min; Max] [Q1; Q3]	XX XX.XX (X.XX) XX.X [XX.X; XX.X] [XX.X; XX.X]	XX XX.XX (X.XX) XX.X [XX.X; XX.X] [XX.X; XX.X]	XX.X

^{*} Standardised difference: rapid interpretation: 0.2-0.3: weak, 0.3-0.8: moderate, >0.8: strong.

Table 14.1.4.3.2: Representativeness of Sample of Patients: Comparison of Non-Included and Included Patients

		Non-included patients* (N=XX)	Included patients (N=XX)	Standardised difference**
Age at inclusion (years)	N	XX	XX	
rige at increasion (years)	Missing data	XX	XX	
	Mean (SD)	XX.XX (X.XX)	XX.XX (X.XX)	XX.X
	Median	XX.X	XX.X	
	[Min; Max]	[XX.X; XX.X]	[XX.X; XX.X]	
	[Q1; Q3]	[XX.X; XX.X]	[XX.X; XX.X]	
Sex	N	XX	XX	
	Missing data	XX	XX	
	Male	XX (XX.X%)	XX (XX.X%)	XX.X
	Female	XX (XX.X%)	XX (XX.X%)	XX.X
Reason for non-inclusion	N	XX		
reason for non metasion	Missing data	XX		
	Patient refusal	XX (XX.X%)		
	Other	XX (XX.X%)		

^{*} data collected in the non-inclusion register.

Listing 14.1.4.3.1: Other Reasons for Non-Inclusion – Non-Included Patients

Centre No.	Registration no.	Age	Sex	Others reasons for non- inclusion
XXXXX	1	XXXXX	XXXXX	XXXXX
	2	XXXXX	XXXXX	XXXXX

^{***} Standardised difference: rapid interpretation: 0.2-0.3: weak, 0.3-0.8: moderate, >0.8: strong.

Table 14.1.4.3.3: Representativeness of the Samples of Patients: Comparison of Patients Lost to Follow-Up and/or Who Discontinued the Study Treatment Early (For a Reason Other than Death) and Patients with Full Follow-Up

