		Patients lost to follow-up and/or dropped out of the study (for reason other than death) (N=XX)	Patients with complete follow- up** (N=XX)	Standardised difference*
Age at inclusion (years)	N Missing data	XX XX	XX XX	
	Missing data Mean (SD)	XX.XX (X.XX)	XX.XX (X.XX)	XX.X
	Median	XX.XX (X.XX) XX.X	XX.X XX.X	AA.A
	[Min; Max]	[XX.X; XX.X]	[XX.X; XX.X]	
	[Q1; Q3]	[XX.X; XX.X]	[XX.X; XX.X]	
Sex	N	XX	XX	
	Missing data	XX	XX	
	Male	XX (XX.X%)	XX (XX.X%)	XX.X
	Female	XX (XX.X%)	XX (XX.X%)	XX.X
ECOG index at inclusion	N	XX	XX	
	Missing data	XX	XX	
	0	XX (XX.X%)	XX(XX.X%)	XX.X
	1	XX (XX.X%)	XX (XX.X%)	XX.X
	2	XX (XX.X%)	XX (XX.X%)	XX.X
	3	XX (XX.X%)	XX (XX.X%)	XX.X
	4	XX (XX.X%)	XX (XX.X%)	XX.X
Group	N	XX	XX	
	Missing data	XX	XX	
	Targeted therapies	XX (XX.X%)	XX (XX.X%)	XX.X
	Other treatments	XX (XX.X%)	XX (XX.X%)	XX.X

The ECOG data = unknown entries were deemed to be missing data.

^{*} Standardised difference rapid interpretation: 0.2-0.3: weak, 0.3-0.8: moderate, >0.8: strong.

^{**} Patients who have complete follow-up (followed up until disease progression, death, end of main treatment ongoing at the time of inclusion or 2-year cutoff date).

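### The lost-versus-complete comparison in SAP 5.4.3 uses a definition of complete follow-up that does not fit overall survival, overlaps the lost group, and conflicts with SAP 6.1.2

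*SAP*

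**What the plan says.** **The comparison.** SAP 5.4.3 sets it out for the reference set: "patients who are lost to follow-up and/or dropped out of the study (for a reason other than death) will be compared to patients with complete" (quote cut short). Complete follow-up means "follow-up until progression, death, end of main treatment ongoing at the time of inclusion or 2-year cutoff date". Standardised differences of 0.2 or less are read as no difference, 0.2 to 0.3 as small, 0.3 to 0.8 as average, and above 0.8 as large.

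**The table.** Table 14.1.4.3.3 (SAP 9.1.4.3) implements this for age, sex, ECOG and treatment group. Its footnote repeats the definition: "Patients who have complete follow-up (followed up until disease progression, death, end of main treatment ongoing at the time of inclusion or 2-year cutoff date". Its title describes the first group as "Patients Lost to Follow-Up and/or Who Discontinued the Study Treatment Early", whereas its column heading refers to dropping out of the study.

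**The protocol.** Section 8.3.1.2 has nearly the same comparator for lost patients, who "will be compared to the patients who are monitored until the event date (progression, death or end of treatment) or the end date of 2" (quote cut before the unit, which is years). It defines lost patients narrowly, as those "who leave the study with no information on whether or not treatment was continued or on death".

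**A different comparator elsewhere.** SAP 6.1.2 says the analyses are to "compare the characteristics of included patients who participated throughout the duration of the study with those patients who were included but were lost to follow-up"; those who stopped the study count with the lost. Protocol 9.1.2 likewise sets "enrolled patients who participate in the whole duration of the study with the enrolled patients who were later lost to follow-up and/or left the study".

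**The endpoints.** In SAP 5.5 and 5.5.1, OS runs from treatment start to death from any cause and is censored at last follow-up or last news. PFS counts events and censoring only while the patient is on the inclusion treatment. SAP 3.3 plans 24 months of follow-up from inclusion whatever happens to treatment. CRF section 3.3 keeps patients in follow-up for 2 years after treatment stops.

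**The concern.** The definition suits PFS as the SAP observes it, because progression or the end of the inclusion treatment closes that observation. It does not suit OS. A patient who stops the inclusion treatment at month 3 and is lost at month 8 is a censored, incomplete case for OS, yet has reached one of the four milestones.

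Losses after progression or treatment stop may well be related to prognosis, and they are the losses that this definition can move into the reference column. If they are moved, a real difference between lost and retained patients can fall below the 0.2 threshold. SAP 5.5.1 itself warns that drop-outs may bias the survival results, and its handling is to censor them. The plan has no other comparison of the characteristics of lost and retained patients.

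**Working it through.** The point concerns a classification rule, so there is no figure in the plan to reproduce. The first step sets the passages side by side. The second and third show size under stated assumptions.

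**1. Which group does a late loss belong to?** Take a patient who progresses at month 5 and is lost at month 8.
- Lost or dropped out for a reason other than death (SAP 5.4.3): yes.
- Complete, because progression was reached (SAP 5.4.3 and table footnote): yes.
- Participated throughout (SAP 6.1.2, Protocol 9.1.2): no.

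No precedence is stated. If the lost group came first, everyone left would have died or reached 2 years, and the progression and end-of-treatment clauses would do nothing. Those clauses have an effect only if late losses go to the complete column, or to both columns.

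**2. How many patients could be affected?** Inputs:
- N = 150 (Protocol 8.1).
- OS median 38 months, from an epidemiological series cited in Protocol section 2, used for illustration only.
- Assumed: PFS median *m* of 9 to 24 months, and loss by 24 months *d* = 10%.
- Assumed: exponential times, with loss independent of outcome.

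Hazards: c = −ln(1−d)/24 = 0.00439; λ_OS = ln2/38 = 0.01824; λ_PFS = ln2/m.

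P(lost before death or 24 months) = c/(c+λ_OS) × [1−exp(−24(c+λ_OS))] = 0.081, or about 12 of 150. The same formula with λ_PFS gives the probability of loss before progression. The remainder is loss after progression.

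| PFS median (months) | Lost before progression | Share of losses after progression | Patients |
|---|---|---|---|
| 9 | 0.046 | 43% | 5.3 |
| 12 | 0.055 | 33% | 4.0 |
| 18 | 0.066 | 19% | 2.3 |
| 24 | 0.073 | 11% | 1.3 |

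With d = 5% or 20% the shares barely move. The counts become 0.7 to 2.6 of 6 lost, or 2.6 to 10.4 of 24 to 25 lost. Treatment stops for other reasons would raise the share.

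**3. What does misplacement do to the standardised difference?** SAP 5.4.3 formula: d = (P1−P2)/√{[P1(1−P1)+P2(1−P2)]/2}. Assumed: 30 of 150 lost, *k* of them after progression or treatment stop, and ECOG ≥1 in 40% of retained patients.

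(a) *Only the late losses differ (70% against 40%).* For k = 15, the lost group as a whole has (15×0.7+15×0.4)/30 = 0.55. A complete column that includes the late losses has (120×0.4+15×0.7)/135 = 0.433.

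| k | Late losses in lost group | In both groups | In complete group |
|---|---|---|---|
| 10 | 0.20 | 0.15 | −0.05 |
| 15 | 0.30 | 0.23 | −0.07 |
| 20 | 0.41 | 0.32 | −0.09 |

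The last column reads as no difference in every row.

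(b) *All losses differ (70% against 40%).* With late losses in the lost group, d = 0.3/√[(0.21+0.24)/2] = 0.63. With them in the complete group, d = 0.58, 0.56 and 0.54 for k = 10, 15 and 20. The label stays average.

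A value of k = 10 of 30 (33%) lies within the range in step 2. The larger values need treatment stops other than progression.

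**The case against.** - **The text does not settle that late losses are counted as complete.** The lost group in SAP 5.4.3 is unrestricted, so a late loss belongs there too. This stands. Counting such patients as complete is the reading that gives every clause a purpose, but it is not the only one.
- **A reader might infer that the check cannot detect attrition bias in OS.** The documents do not support that. Losses before progression or treatment stop are still compared, and case (b) shows selective loss across all drop-outs is still flagged.
- **A reader might also infer that incomplete follow-up is hidden.** It is not. SAP 5.3 and Tables 14.1.3.4 to 14.1.3.7 report drop-out reasons and end-of-study status, with completion of 2-year follow-up shown among those alive. The survival tables show censored patients, with losses separate.
- **The table is modest.** It describes four baseline variables and does not test bias in OS under any definition. Small numbers also limit it: with an assumed 15 lost against 135, the approximate standard error of a standardised difference is √(1/15+1/135) = 0.27, above the 0.2 threshold. This stands, and it limits how much any version of the table can show.
- **The SAP follows the protocol.** Protocol 8.3.1.2 has almost the same comparator. That explains the wording, but Protocol 9.1.2 contradicts it.
- **The mismatch in the table title is partly editorial.** This is fair: the column heading agrees with SAP 5.4.3.

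**Conclusion.** The point holds in a limited form. The comparator in SAP 5.4.3 does not fit OS, overlaps the lost group with no precedence rule, and conflicts with SAP 6.1.2, Protocol 9.1.2 and the title of its own table. These findings need no assumptions.

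The consequence is a diluted check that can miss selective loss confined to the period after progression or treatment stop. In the assumed example, differences of 0.20 to 0.41 become −0.05 to −0.09. Where earlier losses are also selective, 0.63 falls only to 0.54 to 0.58. The number of patients involved is unknown. The 11% to 43% range rests on assumed PFS medians, assumed loss rates and an exponential model, and it excludes treatment stops other than progression.

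Nothing here shows that the OS or PFS estimates are themselves wrong. The defect is in a supporting table, but it is a stated rule that could lead to a reassuring label for OS that the comparison has not earned.

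**What to change.** Make the groups mutually exclusive and specific to each endpoint.
- **OS:** complete means death, or vital status known to the end of the planned 24 months. All others are incomplete. State the origin of the 24 months: SAP 3.3 counts from inclusion and SAP 5.5.1 from treatment start, and these differ for every prevalent patient.
- **PFS:** keep the on-treatment definition in SAP 5.5 and 5.5.1. Complete means progression or death on the inclusion treatment, end of that treatment, or 24 months. Only patients lost before any of these are incomplete.

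Present Table 14.1.4.3.3 once for each endpoint. Align its title, column heading and footnote with SAP 5.4.3 and 6.1.2. Record the departure from Protocol 8.3.1.2 in SAP 5.8. Settle the classification before results are read, so that it is not chosen after the fact.

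The cost is rewording, one extra descriptive table from data already collected, and a recorded departure from the protocol. The primary estimates do not change.

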5.5. Analysis of the Primary Objective

The following parameters will be analysed in the reference set in order to meet the primary objective of the study:

• Progression-free survival at 2 years when receiving the main treatment at the time of inclusion. Progression-free survival is defined by the time between starting treatment (the sequence ongoing at the time of patient inclusion into the study) and the date of

first documented disease progression or all-cause death when receiving the main treatment at the time of inclusion.

- Overall survival rate at 2 years. Overall survival is defined by the time between starting treatment (the sequence ongoing at the time of patient inclusion into the study) and all-cause death.
- Treatment safety (targeted therapies and other treatments) during the prospective period of the study described in terms of treatment discontinuations and the reasons for these, adverse events (graded according to CTCAE version 4.0, May 2009) and any complications of these adverse events. This analysis is described in Section 5.7.

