3.1. Primary objective

The primary objective of this observational study is to describe the real-world outcomes in adult patients treated (targeted therapies and other treatments) for a well-differentiated, unresectable or metastatic, progressive pancreatic neuroendocrine tumour in terms of morbidity and mortality at 2 years. The following parameters will be assessed in order to meet this objective:

- Rate of progression-free survival at 2 years. Progression-free survival is defined as the time between the start of treatment (of the treatment line ongoing at the time the patient was enrolled in the study) and the date of the first disease progression or death, irrespective of the cause.
- Overall survival at 2 years. Overall survival is defined as the time between the start of treatment (of the treatment line ongoing at the time the patient was enrolled in the study) and death, irrespective of the cause.
- Safety of the treatments (targeted therapies and other treatments) defined by instances of treatment discontinuation and the reasons, adverse events (graded according to the 'Common Terminology Criteria for Adverse Events' (CTCAE) version 4.0 of May 2009), and any complications of adverse events.

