5.2.2. Data collection

The data will be collected in an electronic case report form (eCRF). Patients will be indirectly identified by a number that is for the study only (a combination of the site number and patient number).

Questionnaires will be collected at different measuring points:

- When the site is opened: doctor's questionnaire
- On enrolment of patients: at enrolment visit completed by the doctor (collection of retrospective and/or prospective data depending on whether the patient is a prevalent or incident case)
- During patient follow-up: at follow-up visits completed by the doctor (collection of prospective data)
- If the study is stopped: at the anticipated end of study visit, completed by the doctor

Doctors' data

Each participating doctor will complete the following information:

- Characteristics of the site (type of site, active patient list).

Patient data

Patients who are enrolled will have their indirectly nominative medical data collected (patient questionnaires completed by the doctor) at enrolment and at each follow-up visit, around every 2 - 3 months in line with the usual schedule of consultations for tumour assessment at the site.

The study will include a phase of retrospective and/or prospective data collection (Table 2) depending on whether patient is a prevalent case (systemic treatment started before the enrolment visit) or incident case (systemic treatment for the study started at the enrolment visit).

All patients will have prospective data collected irrespective of the treatment line ongoing and this applies until the end of their follow-up within the study (2 years), or until the patient leaves the study, or, for safety data, until 28 days after the patient has stopped the treatment.

All prevalent case patients will have safety data collected retrospectively.

The methods of declaring safety data are set out in paragraph 7. Pharmacovigilance

	enrolment.	
	- For all other treatments ongoing at enrolment (Sunitinib, chemotherapy, somatostatin analogues, radionuclide therapy or interferon alpha), adverse events will be recorded retrospectively:	
	 If they are clearly related to a Pfizer product and occurred after the first treatment line was started and before enrolment. 	

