8.3.2. Analysis of the objectives

8.3.2.1. Analysis of the primary objective

The primary objective of this observational study is to describe the real-world outcomes of adult patients treated (with targeted therapies and other treatments) for a well-differentiated unresectable or metastatic progressive pancreatic neuroendocrine tumour in terms of morbidity and mortality at 2 years.

The following parameters will be assessed in order to meet this objective:

- Rate of progression-free survival at 2 years. Progression-free survival is defined as the time between the start of treatment (of the treatment line ongoing at the time the patient was enrolled in the study) and the date of the first documented disease progression or death, irrespective of the cause.
- Rate of overall survival at 2 years. Overall survival is defined as the time between the start of treatment (of the treatment line ongoing at the time the patient was enrolled in the study) and death, irrespective of the cause.

[figure not shown]
Progression-free survival and overall survival will be estimated using the Kaplan-Meier method. The survival S(t) function will be the probability that the event of interest (progression or death respectively) does not occur before the date t. This function will be represented in a graph using a survival curve that will include 95% confidence intervals, estimated using Rothman's formula.

Survival until progression will be estimated taking into account the date of initiation (of the treatment line ongoing at enrolment of the patient) of the targeted therapy or other treatment (as defined in this study) and the event date, i.e. the date of progression or of death. Patients with no event or who are lost to follow-up will be censored at the last date they are known to be alive.

Overall survival will be estimated considering the date of origin to be the date of initiation (of the treatment line ongoing at enrolment of the patient) of the targeted therapy or other treatment, and the event date to be the date of death. Patients with no event or who are lost to follow-up or alive at the end of the study will be censored at the last date they are known to be alive.

These survival rates will be estimated and presented for each of the groups of interest:

Targeted therapy group (with an estimate for the everolimus and sunitinib sub-groups)

Other treatments group (with estimates for the sub-groups if there are sufficient total numbers)

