3.1 Tumour assessment			
Examination date: ————————————————————————————————————			
Imaging examination performed for tumour assessment (tick all that apply): ☐ CT scan ☐ MRI ☐ PET scan ☐ Octreoscan ☐ Ultrasound ☐ Other, please state:			
Radiological response to treatment in the investigator's opinion (based on RECIST criteria) CR (Complete response) PR (Partial response) SD (Stable disease) PD (Progressive disease) Date of progression:			
Clinical response in investigator's opinion: ☐ Yes ☐ No ☐ Progressive disease Date of progression: ☐ / ☐ / ☐ / ☐ (DD/MM/YYYY) ☐ Stable disease ☐ Response			

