3.3 Therapeutic management since last tumour assessment

Since the last documented visit, the cancer treatment may have been continued or may have changed on one or more occasions. The participating doctor must enter all of the cancer treatment lines prescribed to the patient, and then complete the corresponding screens.

then complete the corresponding screens.		
Therapeutic management since the last documented tumour assessment visit on [date of the last documented visit] and up to and including today's visit:		
If a treatment was "ongoing" at the end of the previous visit (will be checked by the eCRF): Treatment with [name of treatment] that was ongoing at the previous visit continued If treatment continued: Is [combined treatment entered] being continued? If no, reason for stopping [combined treatment entered]: Adverse event* Patient's decision Doctor's decision Other, please state:		
Have any new combined treatments been started since the last visit? $\ \square$ Yes $\ \square$ No		
If yes, which ones? A somatostatin analogue Please state: Careotide Lanreotide Other treatment, please state: 2)		
☐ Treatment with [name of treatment] that was ongoing at previous visit stopped definitively		
If stopped, Date stopped definitively (see Table 5) Reason for stopping treatment (see Table 5) Was [combined treatment entered] still ongoing on the date when [name of the treatment line stopped] was stopped?		
Has a new treatment line been put in place? ☐ Yes ☐ No If yes, please describe all new lines of cancer treatment put in place since the last tumour assessment visit, including the treatment in place at the end of today's visit (see Table 5). If No, if a period of treatment abstention is extended, the patient continues to be followed for 2 years as planned (unless deceased or lost to follow-up).		
If no treatment was "ongoing" at the end of the previous visit (will be checked by the eCRF): Treatment abstention extended (apart from temporary treatment interruptions) If Extended, if a period of treatment abstention is extended, the patient continues to be followed for 2 years as planned (unless deceased or lost to follow-up). New treatment line resumed If Resumed, please describe all new lines of cancer treatment put in place since the last tumour assessment visit, including the treatment in place at the end of today's visit (see Table 5).		

Observational study protocol $final\ version\ of\ 17/07/2018$

Table 5 – Therapeutic management				

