Treatment	Start date	Date stopped	If stopped, reason	
		definitively		
Treatment ongoing at previous visit	Start date	- If stopped, date	If stopped, Reason	
(auto)	(auto)	stopped	☐ Disease progression	
			☐ AE	
		- If not, Ongoing.	If AE, has an AE reporting	
			form been completed?:	
			☐ Yes ☐ No	
			If no, please report the AE*	
			☐ Patient's decision	
			☐ Doctor's decision, if so	
			please state why:	
			☐ Cumulative dose reached	
			☐ Scheduled stop	
			☐ Optimum response☐ Other, please state:	
			☐ Other, please state:	
			Lost to follow-up	
			☐ Death → redirects to the	
			Anticipated end of study	
			questionnaire	
Targeted therapy	/ /	- If stopped, date	If stopped, Reason	
everolimus		stopped	☐ Disease progression	
sunitinib		/ /	☐ AE	
Chemotherapy		- If not, Ongoing.	If AE, has an AE reporting	
□ 5 FU		, , , ,	form been completed?	
☐ Capecitabine (Xeloda®)			☐ Yes ☐ No	
☐ Doxorubicin (Adriamycin®)			If no, please report the AE*	
☐ Streptozocin (Zanosar®)			☐ Patient's decision	
☐ Temolozomide (Temodal®)			☐ Doctor's decision, if so	
☐ Dacarbazine (Deticene®)			please state why:	
☐ Oxaliplatin (Eloxatin®)			☐ Cumulative dose reached	
☐ Gemcitabine (Gemzar®)			☐ Scheduled stop	
□ Cisplatin			Optimum response	
□ VP-16			☐ Other, please state:	
Other, please state:			District fallows	
Somatostatin analogues Octreotide			☐ Lost to follow-up	
☐ Lanreotide			☐ Death → redirects to the	
Interferon alpha			Anticipated end of study questionnaire	
☐ Interferon alpha			questionnaire	
Radionuclide therapy				
☐ Radionuclide therapy				
Other				
☐ Other, please state:				
(lines may be added if there are more tr	eatments to enter)			
* If there has been an adverse event, p	lease complete the	safety section of the CRF	within the stated timeframe	
If no "ongoing" treatment is entered of	and if the patient is	s not deceased or lost to	follow-up (will be checked by the	
eCRF):				
Is the patient receiving a new treatmer			-	
If yes, please describe the new treatmen	nt line targeting the	tumour that was put in pl	ace at today's visit (see Table 5)	
If not, the following is displayed:	udu la aat at 3	ara Diagga rangas sha fa	llow up visit at the most town	
The patient follow-up phase in the st assessment visit.	uuy is set at 2 ye	ars. Frease repeat the 10	now-up visit at the next tumour	
מססכססווופווג עוסול.				
For each line of cancer treatment enter	ed, the participatin	g doctor will be redirected	d to the corresponding screen.	

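### The SAP restricts primary PFS to events on the inclusion treatment and moves its censoring date, declares neither change, and plans no analysis stated to use the protocol's event rule

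*SAP*

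**What the plan says.** Protocol 3.1 ends PFS at "the date of the first disease progression or death, irrespective of the cause". Protocol 8.3.2.1 repeats this as "the date of the first documented disease progression or death, irrespective of the cause" and adds the censoring rule: "Patients with no event or who are lost to follow-up will be censored at the last date they are known to be alive". Neither section requires the patient still to be on the treatment held at enrolment.

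SAP 5.5 ends PFS at the "first documented disease progression or all-cause death when receiving the main treatment at the time of inclusion". The table in SAP 5.5.1 applies the same condition to the event date and to censoring, and the text below it applies the condition to the choice of progression. A footnote to Tables 14.2.1.1 and 14.2.1.2 ties events to the main treatment at inclusion. Event-free patients are censored at their last assessment on that treatment or, if no assessment date exists, at its discontinuation date. Stopping the main treatment for progression counts as an event.

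SAP 2 describes the plan as consistent with protocol version 13. SAP 5.8 lists one amendment, the confidence-interval formula.

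**The concern.** A patient who stops the inclusion treatment for an adverse event, by choice, on schedule or after a good response, and who later progresses or dies, has a PFS event under the protocol. Under the SAP that patient is censored at the last on-treatment assessment. The SAP therefore estimates PFS while on the inclusion treatment and reports it as the protocol's primary parameter.

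The health authority asked for the two-year course of treated patients (Protocol 2, justification for the study). On-treatment PFS describes one treatment interval, which is a different quantity. Because 5.8 does not mention the change, a reader comparing the report with the protocol would assume the two match.

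**Working it through.** **1. The two definitions side by side**

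| | Protocol 3.1 and 8.3.2.1 | SAP 5.5, 5.5.1, footnote in 9.2 |
|---|---|---|
| Event | First progression or any death | First progression or any death, only while on the inclusion treatment |
| Censoring | Last date known alive | Last assessment on the inclusion treatment, else its stop date |
| Declared in SAP 5.8 | n/a | No |

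**2. Is the protocol's event rule used elsewhere in the SAP?**

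- The subgroup analyses in 5.9.7 concern PFS of the inclusion treatment and follow the main method.
- The per-line analyses in 5.9.7 start at each line's own start date and censor within the line.
- The supportive analysis in incident patients (5.5.1) changes the population and the estimator only.
- Supportive Table 14.2.2.9.1, and PFS in patients ever given targeted therapy (Tables 14.2.2.6.17 and 14.2.2.6.18), state no event rule of their own.
- Overall survival keeps every death but no progressions.
- Tables 14.2.2.5.1, 14.3.1.7 and 14.3.1.8 and Listings 16.2.4 and 16.2.5 show stops and their reasons, not PFS.

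No planned analysis is stated to use the protocol's event rule.

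**3. Are the data collected?** Protocol 5.2.2: "All patients will have prospective data collected irrespective of the treatment line ongoing", to 2 years. CRF 3.3: "if a period of treatment abstention is extended, the patient continues to be followed for 2 years as planned". CRF 3.1 has a dated entry at each assessment visit: "PD (Progressive disease) Date of progression".

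**4. The plan's own precision figure.** The half-width at the median is 1.96 × √(0.25/n), which gives 0.113 at n=75, 0.080 at n=150 and 0.052 at n=360, as stated in Protocol 8.1 and SAP 4.2. The formula assumes no right censoring before the median. Censoring at the end of the inclusion treatment adds some.

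**5. Illustrative size.** The documents give no median PFS, stop rate or post-stop hazard, so every such input is an assumption:

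- exponential PFS with median m = 8, 11 or 18 months, so h = ln2/m
- non-progression stops at c = 1, 3 or 5% per month
- hazard multiplied by k = 0.5, 0.75, 1, 1.5 or 2 after stopping

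This makes 3 × 3 × 5 = 45 cells. All patients enter at treatment start, with no loss to follow-up.

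- SAP rule: S(24) = exp(−24h)
- Protocol event rule: S(24) = exp(−24(h+c)) + ∫₀²⁴ c·exp(−(h+c)s)·exp(−kh(24−s)) ds

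Example with m=11, c=0.03, k=2: h = 0.0630. The SAP rule gives 0.220. The protocol rule gives 0.107 + 0.053 = 0.161. The difference is +6.0 points.

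| Stops per month | Stopped event-free by month 24 | SAP minus protocol rule, one common k | Half the stops k=0.5, half k=2 | First events left out in that mix |
|---|---|---|---|---|
| 1% | 9–14% | −2.4 to +3.0 points | −0.3 to +0.3 | 7–10% (9–10 per 150 patients) |
| 3% | 24–35% | −6.4 to +7.8 | −0.8 to +0.8 | 20–26% (24–26) |
| 5% | 35–50% | −9.3 to +11.2 | −1.2 to +1.0 | 29–38% (35–38) |

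At k=1 the difference is 0 throughout. With 75% of stops at k=0.5 it is −4.9 to −1.0 over all medians and rates; with 75% at k=2 it is +0.7 to +6.1. Events left out = [1 − S_protocol(24)] − h/(h+c) × [1 − exp(−24(h+c))].

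**6. Yardstick.** The binomial 95% half-width at S(24) is 1.96 × √(S(1−S)/n), ignoring censoring and truncation. For S = 0.125, 0.22 and 0.397 it is 5.3, 6.6 and 7.8 points at n=150, and 7.5, 9.4 and 11.1 at n=75. The difference exceeds it in 7 of 45 cells at n=150 and in 2 at n=75. Five cells exceed 8 points, all at 5% per month.

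**The case against.** The SAP states its rule openly and repeatedly, so a reader of the main PFS tables is told which events count. Protocol 8.3.1.2 names end of treatment beside progression and death when it describes patients with complete follow-up, and SAP 5.4.3 does the same, so the on-treatment idea has a source in the protocol. Those sections define a comparison group for patients lost to follow-up, however, and 8.3.2.1 defines the endpoint. An open rule in the SAP still replaces the protocol's parameter if the change is not declared.

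Censoring at the last assessment is defensible in itself, and the fix below keeps it. The fault is that it is undeclared and tied to the inclusion treatment. The missing-data paragraph in SAP 5.5.1 also censors patients lost to follow-up at their last follow-up time, which conflicts with the table in the same section.

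The size is uncertain, and this part of the objection stands. All inputs are assumed. The cells above the n=150 yardstick all have k at 0.5 or 2, and six of the seven need 5% stops per month. No mixed-stop scenario exceeds the yardstick. SAP 5.5.1 says treatment is changed after progression, and such stops already count as events, so only other stops matter. After a switch, progression may also be judged against a new baseline, and later events reflect later drugs. These are reasons to keep on-treatment PFS as a labelled analysis; they do not justify omitting the protocol's.

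**Conclusion.** The concern holds and must be fixed. The SAP replaces the event rule and the censoring date of a primary parameter without declaring either, and no planned analysis is stated to restore the protocol's event rule. This rests on the texts alone and needs no assumption.

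The direction and size of the effect on 24-month PFS cannot be determined from the documents. CRF Table 5 allows stops for adverse events and for "Optimum response", which could pull in opposite directions. The ranges in the working are conditional on the assumed medians, stop rates and hazard multipliers. A near-zero net difference would not make the two quantities the same, because a material share of first events could still be left out. The point concerns PFS only.

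**What to change.** 1. Report PFS under the protocol's event rule (first progression or death from any cause during follow-up, whether or not the inclusion treatment has stopped), overall and for the treatment groups, as the protocol's primary parameter. Keep on-treatment PFS as a separately labelled analysis. If the sponsor prefers on-treatment PFS as the main analysis, the protocol-rule version must at least be a named analysis beside it.
2. List the event-rule and censoring-date changes in SAP 5.8 with reasons, and reconcile the two censoring statements for patients lost to follow-up in 5.5.1.
3. Specify the derivation. Take the first radiological or clinical progression recorded after inclusion on any line, a stop of any line for progression, or death, whichever comes first. Keep the patient in the inclusion-treatment group, with time from the start of the inclusion line and the same left-truncation method. Censor at the last tumour or clinical assessment on any line, and declare this in 5.8 as a departure from Protocol 8.3.2.1. Report how many first events fall after the stop, split by whether a new line had begun.
4. In the PFS tables, split patients censored for other reasons by the reason for stopping the inclusion treatment.

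The cost is SAP wording, the 5.8 entries, one programmed derivation and a protocol-rule version of Tables 14.2.1.1 to 14.2.1.4. The 14.2.2.6 subgroup tables can stay on-treatment if labelled. No new data collection is needed. The drawback is that the added figure includes progressions on later lines, so it describes the patient's course rather than one drug.
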